Participants will be hospitalized for at least 3 days or up to 7 days, depending on the participant convenience. After discharge, subjects will return daily to the Clinical Center for further assessments until Day 7. The duration of involvement in the study from day 0 (day of administration of first PZQ dose) will be 7 days. The start of the trial is defined as the date of the first visit (i.e. screening visit) of the first participant. The end of the trial is the date of the last visit of the last participant.

Potential risks for participants

Phlebotomy

The maximum volume of blood drawn over the study period is approximately 61 ml over 7 days. Additional blood samples could be required for safety reasons. However, this volume should not compromise these otherwise healthy participants. There may be minor bruising, local tenderness or presyncopal symptoms associated with venepuncture, which will not be documented as AEs if they occur. Rare side effects are infections, thrombophlebitis and neural lesions. In the case a participant develops severe discomfort from repeated venepunctures, and only with the recommendation/concurrence of the clinical team, an intravenous catheter could be inserted in one of the upper limbs of the participant to take the remaining blood samples as per protocol. An additional 2 mL of blood will be taken with each blood drawn when using the intravenous catheter. The participant will be informed about this extra volume of blood to be drawn before the catheter insertion.

Praziquantel

Side effects of praziquantel include nausea ($\geq 10\%$), vomiting ($\geq 10\%$), gastrointestinal and abdominal pain ($\geq 10\%$), headache ($\geq 10\%$), drowsiness ($\geq 10\%$), urticaria ($\geq 10\%$), diarrhoea

(<10%), anorexia (<10%), dizziness (<10%), somnolence (<10%), fever (<10%), rash (<10%), myalgia (<10%), unspecific arrhythmia (<0.0001%), pruritus (<0.0001%), seizure (<0.0001%), allergic reaction (<0.0001%), eosinophilia (<0.0001%) (41).

Potential benefits for participants

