Exceptions from this rule can be made if the problem, if a clinician is convinced the respective sign/symptom/disease has become much different in severity/intensity, quality etc.

Grading of adverse events

The investigator will assess the **severity/intensity** of the adverse event using the following terms:

Table 3: Severity of Adverse Events

Grade 1	Mild	Awareness of sign or symptom, but easily tolerated; Transient or mild discomfort (< 48 hours); no medical intervention/therapy required
Grade 2	Moderate	Enough discomfort to cause interference with usual activity; Mild to moderate limitation in activity* - some assistance may be needed; no or minimal medical intervention/therapy required
Grade 3	Severe	Incapacitating with inability to work or do usual activity; Marked limitation in activity**, some assistance usually required; medical intervention/therapy required, hospitalisations possible
Grade 4	Life-threatening	Note: this must also be reported as Serious Adverse Event; Extreme limitation in activity, significant assistance required; significant medical intervention/therapy required, hospitalisation or hospice care probable
Grade 5	Death	Note: this must also be reported as Serious Adverse Event

*Includes limitation in instrumental activities of life: preparing meals, shopping for groceries or clothes etc

**Includes limitation in self-care activities of life: bathing/showering, dressing/undressing, feeding self, using the toilet etc

Serious or Life-Threatening AEs

ANY clinical event deemed by the clinician to be serious or life-threatening should be considered a grade 4 event. Clinical events considered to be serious or life-threatening include, but are not limited to: seizures, coma, tetany, diabetic ketoacidosis, disseminated intravascular coagulation, diffuse petechiae, paralysis, acute psychosis, severe depression.

Causality assessment between study medication and AE

Afterwards the investigator has to decide a term for describing the relationship to the study drug:

Table 4: Relationship to Study Drug (Causality assessment)

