Procedures for unblinding in case of safety issues

If it is medically imperative to know which trial medication the subject is receiving, the investigator or authorized person should unblind the treatment allocation. A trial-specific SOP that describes unblinding in detail will be implemented before trial initiation.

Suspected Unexpected Serious Adverse Reaction (SUSAR)

Upon receiving the SAE form, the sponsor and medical monitor will discuss and decide on the expectedness of the SAE. Any AE that is mentioned in the investigator brochure or summary of product characteristics (SmPCs) is considered ‘expected’. An AE not mentioned in the investigator brochure or SmPC is considered ‘unexpected’. A SUSAR is an SAE that is both ‘unexpected’ and at least ‘possibly related’ to the study medication (i.e. if there is no association to the study medication it is no SUSAR).

The Principal Investigator (PI) will report all SUSARs to the Ethics Committee (EC) within 7 calendar days in case of Fatal and life-threatening SUSARs and within 15 calendar days in case of SUSARs that are not fatal or life threatening.

The PI will also inform all investigators concerned of relevant information about SUSARs that could adversely affect the safety of participants.

Laboratory safety

When grading abnormal laboratory values the investigator needs to first judge if the abnormal lab value entails clinical significance. If this is the case (i.e. **abnormal lab value & clinical significance**) then routine grading shall be performed as explained above for clinical symptoms (by primarily using ‘Table 3 Severity of Adverse Events’). In case the laboratory value is outside of local laboratory ranges, but **not clinically significant** then grading shall be performed according to

modified 'Common Terminology Criteria for Adverse Events (CTCAE) v5.0'. Tables with modified CTCAE criteria are attached in ANNEX 1.

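### Expectedness rests on mention alone, so a fatal or life-threatening event recorded under a listed term is not a SUSAR and has no fixed ethics committee deadline

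*Protocol*

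**What the plan says.** The rule stands in the protocol section on Suspected Unexpected Serious Adverse Reactions. After an SAE form arrives, "the sponsor and medical monitor will discuss and decide on the expectedness of the SAE". The criterion then given is mention in the product documents, stated in both directions: "Any AE that is mentioned in the investigator brochure or summary of product characteristics (SmPCs) is considered" expected; the converse is that "An AE not mentioned in the investigator brochure or SmPC is considered" unexpected. The SUSAR definition builds on this: "A SUSAR is an SAE that is both" unexpected and judged to have at least a possible link with the study drug.

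The dated duties towards the ethics committee follow from that status. For the gravest cases the text reads: "The Principal Investigator (PI) will report all SUSARs to the Ethics Committee (EC) within 7 calendar days in case of Fatal and life-threatening SUSARs". For the remainder the limit is 15 calendar days. The same section has the principal investigator pass relevant SUSAR information to the investigators concerned.

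Two other places bear on this:

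- Under Potential risks for participants, the Praziquantel paragraph includes "unspecific arrhythmia (<0.0001%), pruritus (<0.0001%), seizure (<0.0001%), allergic reaction (<0.0001" per cent) among the listed side effects. It cites reference 41, the manufacturer's product information.
- Under Serious or Life-Threatening AEs, the protocol states: "Clinical events considered to be serious or life-threatening include, but are not limited to: seizures, coma", and further conditions. Such events are to be graded 4, and Table 3 requires grade 4 events to be reported as SAEs.

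**The concern.** Expectedness normally asks whether the event that occurred, in its nature, severity and outcome, is already described for the drug. Here it asks only whether the term appears. A death from an arrhythmia and an arrhythmia from which the participant recovers get the same answer, because the term is listed.

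The section also sets up a faster track for fatal and life-threatening SUSARs, but severity is consulted only after mention has decided whether any deadline applies. For a listed term, the faster track cannot be reached. At stake are three things: the SUSAR label, the fixed ethics committee deadline, and the onward information to investigators. They would be lost for events that are among the gravest the protocol itself names for praziquantel.

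**Working it through.** The plan gives no figure on this point and no arithmetic applies. The check is to follow the written rules for an SAE judged at least possibly related to praziquantel.

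1. **Is the term mentioned?** The Praziquantel risk paragraph lists seizure, unspecific arrhythmia and allergic reaction, citing the product information. For these three terms the answer is yes.
2. **Expected or unexpected?** Under the SUSAR section, mentioned means expected and only an unmentioned event is unexpected.
3. **SUSAR or not?** A SUSAR must be unexpected. A listed event therefore fails, whatever its course.
4. **Which ethics committee deadline?** The 7- and 15-day limits attach to SUSARs only.

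Four cases set side by side:

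| SAE, at least possibly related | Term listed | Class | SUSAR | Ethics committee deadline in the SUSAR section |
|---|---|---|---|---|
| Prolongs hospital stay, recovers | yes | expected | no | none |
| Fatal | yes | expected | no | none |
| Prolongs hospital stay, recovers | no | unexpected | yes | 15 days |
| Fatal | no | unexpected | yes | 7 days |

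The first two rows are identical, so outcome has no effect once the term is listed. A fatal listed event also has no dated ethics committee duty, while a non-fatal unlisted one has 15 days.

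Next, is there a qualifier elsewhere? The sections on definitions, grading, causality, SAE notification and SUSARs contain none that makes expectedness depend on severity, specificity or outcome. Severity is graded in Table 3, but that grade is not carried into the expectedness test.

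Finally, what still happens to such an event? The SAE part of the notification section applies regardless of causality and does not mention expectedness:

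- Forms go to the sponsor, medical monitor, clinical monitor and study coordinator within 24 hours.
- The medical monitor is contacted the same day for a death or a life-threatening event.
- Follow-up of fatal or life-threatening events keeps the 24-hour timeline.
- The ethics committees are told of any SAE, or as local regulation provides, with no number of days given.

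So the 24-hour and same-day duties survive. The fixed ethics committee deadline, the SUSAR classification and the duty to inform investigators do not.

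**The case against.** The strongest reply is that nothing is hidden. Every SAE reaches the sponsor and medical monitor within 24 hours, the ethics committees are informed, and the Medical monitor section provides an independent clinician permanently on site. No treatment decision in the protocol depends on SUSAR status. In a single-centre trial the duty to inform investigators adds little. All of this stands, and it limits the point to a classification and a missing number of days.

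It also rules out some stronger readings:

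- **That such events can never be SUSARs.** This is not shown beyond events recorded under a listed term. The risk paragraph does not name anaphylaxis or status epilepticus, and its arrhythmia term is a general one. The protocol asks for symptoms to be grouped into a diagnosis where possible, so a specific diagnosis might be recorded and judged not mentioned. The sponsor and medical monitor decide each case. The text, however, gives them no criterion for drawing that line.
- **That the 7- and 15-day limits are the only dated expedited duties.** They are not, because the general SAE procedure sets 24-hour and same-day duties. They are the only dated duties towards the ethics committee.
- **That the listed rates, below 0.0001%, make a single case a signal which the rule suppresses.** The defect concerns severity, specificity and outcome, not frequency. A remedy on those grounds would still class a rare event as expected if it matched the listing. The rates do not measure the problem.

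It is also fair to say that the investigator brochure and SmPC are not shown. If they list severe forms or fatal outcomes, those events would be expected under a better rule too.

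**Conclusion.** The point holds in limited form and is minor. As written, the rule gives a fatal or life-threatening event the same class as a mild one whenever it is recorded under a listed term, and so removes it from the 7- and 15-day ethics committee deadlines. This is a rule stated in full that classifies wrongly, rather than a detail left for another document.

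The conclusion rests on two assumptions: that the operative product documents list the three terms as the protocol's summary says, and that the event is recorded under the listed term rather than a more specific diagnosis. Sample size, endpoints and the primary analysis are unaffected.

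**What to change.** Replace the mention test in the SUSAR section with two sentences:

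1. An SAE is expected only if its nature, severity, specificity and outcome are consistent with the listing in one named reference safety document, identified by title and version.
2. An event that is more specific or more severe than the listed term, or that has a fatal or life-threatening outcome not itself listed, is unexpected.

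Naming one document matters because the section refers to an investigator brochure or an SmPC without identifying either, while the reference list holds two manufacturer documents (28 and 41). The sponsor and medical monitor remain the deciders, and the 24-hour SAE procedure stays as it is.

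The cost is the wording itself and occasionally one more expedited report in a trial of 44 participants.

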Annex 1: Grading of abnormal lab values which are ‘not clinically significant’

Laboratory values and grading:

Table 5 Biochemistry Values and Grading

	Biochemistry (modified CTCAE v5)			
Variable	Grade 1	Moderate Grade 2	Severe Grade 3	Potentially Life Threatening Grade 4
ALT (GPT)	None	>3.0 – 5.0 ULN if baseline was normal; baseline was normal; >3.0 – 5.0 x baseline if baseline was abnormal	>5.0 – 20.0 x ULN if baseline was normal; baseline was normal; >5.0 – 20.0 x baseline if baseline was abnormal	> 20.0 x ULN if baseline was normal; baseline was normal; > 20.0 x baseline if baseline was abnormal
AST (GOT)	None	>3.0 – 5.0 ULN if baseline was normal; >3.0 – 5.0 x baseline if baseline was abnormal	>5.0 – 20.0 x ULN if baseline was normal; baseline was normal; >5.0 – 20.0 x baseline if baseline was abnormal	> 20.0 x ULN if baseline was normal; baseline was normal; > 20.0 x baseline if baseline was abnormal
Alkaline Phosphatase	None	>2.5 – 5.0 ULN if baseline was normal; >2.5 – 5.0 x baseline if baseline was abnormal	>5.0 – 20.0 x ULN if baseline was normal; baseline was normal; >5.0 – 20.0 x baseline if baseline was abnormal	> 20.0 x ULN if baseline was normal; baseline was normal; > 20.0 x baseline if baseline was abnormal
Total Bilirubin	None	>1.5 – 3.0 ULN if baseline was normal; >1.5 – 3.0 x baseline if baseline was abnormal	>3.0 – 10.0 x ULN if baseline was normal; baseline was normal; >3.0 – 10.0 x baseline if baseline was abnormal	> 10.0 x ULN if baseline was normal; baseline was normal; > 10.0 x baseline if baseline was abnormal

Albumin	None	<3 - 2 g/dL; <30 - 20 g/L	<2 g/dL; <20 g/L	Life-threatening Death consequences; urgent intervention indicated
Creatine Kinase	None	>2.5 x ULN - 5 x ULN	>5 x ULN - 10 x ULN	>10 x ULN
Sodium (Hypernatremia)	None	>150 - 155 mmol/L; intervention initiated	>155 - 160 mmol/L; hospitalization indicated	>160 mmol/L; life-threatening consequences
Sodium (Hyponatremia)	None	125-129 mmol/L and asymptomatic	125-129 mmol/L symptomatic; 120-124 mmol/L regardless of symptoms	<120 mmol/L; life-threatening consequences
Glucose (Hyperglycemia)	None	Change in daily management from baseline for a diabetic; oral antiglycemic agent initiated; workup for diabetes	Insulin therapy initiated; hospitalization indicated	life-threatening consequences; urgent intervention indicated

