Glucose (Hypoglycemia)	None	<55 - 40 mg/dL; <3.0 - 2.2 mmol/L	<40 - 30 mg/dL; <2.2 - 1.7 mmol/L	<30 mg/dL; <1.7 mmol/L; life-threatening consequences; seizures
LDH	None	>3 x ULN	-	-
Potassium (Hyperkalemia)	None	>5.5 - 6.0 mmol/L; intervention initiated	>6.0 - 7.0 mmol/L; hospitalization indicated	>7.0 mmol/L; life-threatening consequences
Potassium (Hypokalemia)	None	Symptomatic with <LLN - 3.0 mmol/L; intervention indicated	<3.0 - 2.5 mmol/L; hospitalization indicated	<2.5 mmol/L; life-threatening consequences

Creatinine	None	>1.5 - 3.0 x baseline; >1.5 - 3.0 x ULN	>3.0 x baseline; >3.0 - 6.0 x ULN	>6.0 x ULN
Urea* (Blood Nitrogen Urea [BUN])	None	2.6 - 5 x ULN	5.1 - 10 x ULN	> 10 x ULN

* Ranges for BUN taken from Division Of Microbiology And Infectious Diseases (DMID) as not available in CTCAE

v5

Laboratory values and grading:

Table 6 Hematology Values and Grading

	Haematology (modified CTCAE v5)			
Variable	Grade 1	Moderate Grade 2	Severe Grade 3	Potentially Life Threatening Grade 4
Haemoglobin	None		< 8.0 g/dL; < 4.9 mmol/L; < 80 g/L; transfusion indicated	Life-threatening consequences; urgent intervention indicated
Leukocytes (WBC) [decreased]	None	<3000 - 2000/mm ³ ; <3.0 - 2.0 x 10 ⁹ /L	<2000 - 1000/mm ³ ; <2.0 - 1.0 x 10 ⁹ /L	<1000/mm ³ ; <1.0 x 10 ⁹ /L
Leukocytes (WBC) [increased]	None	-	>100,000/mm ³	Clinical manifestations of leucostasis; urgent intervention indicated
Lymphocytes [decreased]	None	<800 - 500/mm ³ ; <0.8 - 0.5 x 10 ⁹ /L	<500 - 200/mm ³ ; <0.5 - 0.2 x 10 ⁹ /L	<200/mm ³ ; <0.2 x 10 ⁹ /L
Lymphocytes [increased]	None	>4000/mm ³ - 20,000/mm ³	>20,000/mm ³	-

Neutrophils [decreased]	None	<1500 - 1000/mm ³ ; <1.5 - 1.0 x 10 ⁹ /L	<1000 - 500/mm ³ ; <1.0 - 0.5 x 10 ⁹ /L	<500/mm ³ ; <0.5 x 10 ⁹ /L
Platelet count [decreased]	None		<50,000 - 25,000/mm ³ ; <50.0 - 25.0 x 10 ⁹ /L	<25,000/mm ³ ; <25.0 x 10 ⁹ /L

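### Laboratory values are graded on two unlinked scales chosen by a prior judgement of clinical significance, so an identical value can get a lower grade when it is judged significant

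*Protocol*

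**What the plan says.** In the protocol's Laboratory safety section, grading starts with a judgement: "the investigator needs to first judge if the abnormal lab value entails clinical significance". That answer selects the scale.

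- **Clinically significant:** "then routine grading shall be performed as explained above for clinical symptoms", with Table 3 as the main tool.
- **Outside the local range but not clinically significant:** "then grading shall be performed according to" a modified CTCAE v5.0, set out in Annex 1.

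Table 3 (Grading of adverse events) has no laboratory limits. Its Grade 1 reads "Awareness of sign or symptom, but easily tolerated; Transient or mild discomfort (< 48 hours); no medical intervention/therapy required". Grade 2 adds interference with activity and allows no or minimal intervention. Grade 3 opens with "Incapacitating with inability to work or do usual activity" and presumes that treatment is needed.

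Annex 1 is headed "Grading of abnormal lab values which are" not clinically significant. Most of its cells are numeric. For ALT and AST with a normal baseline, Grade 2 is above 3 to 5 × ULN, Grade 3 above 5 to 20 × ULN and Grade 4 above 20 × ULN. The Grade 1 column is empty for every analyte. Some cells add or substitute a clinical consequence, for example ">7.0 mmol/L; life-threatening consequences" for potassium at Grade 4.

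**The concern.** A severity grade should rise with the importance of the finding. Here the investigator's opinion does not adjust the grade. It moves the value to a different scale, and nothing makes the two scales agree. Laboratory abnormalities are often silent, so a scale built on discomfort and activity tends to place them low. An asymptomatic liver enzyme rise that the investigator takes seriously could then be listed as mild, while the same rise dismissed as unimportant is listed as severe.

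Grades are assigned at the site and entered in the eCRF within 24 hours, and AE intensity is reviewed at the source document meetings, so the rule acts before any analysis plan does. With 22 participants per arm, a few events graded on different scales would visibly change a table of AEs by severity.

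**Working it through.** The protocol gives no figure to reproduce. The check is to put one laboratory value through both branches and compare the grades. Inputs are Table 3, the ALT row of Table 5 and the platelet row of Table 6. Each case assumes no symptoms, and a normal baseline for ALT. The first Table 3 grade assumes no treatment. The second, where given, assumes that minimal intervention alone is enough for Grade 2, which is generous because that grade also describes interference with activity.

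| Value | Not significant (Annex 1) | Significant (Table 3) | Significant minus not significant |
|---|---|---|---|
| ALT 2 × ULN | no grade | at least 1 | higher, as expected |
| ALT 4 × ULN | 2 | 1, or 2 | −1, or 0 |
| ALT 8 × ULN | 3 | 1, or 2 | −2, or −1 |
| Platelets 20,000/mm³ | 4 | 1, or 4 if deemed serious or life-threatening | −3, or 0 |

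1. ALT 2 × ULN lies below the Annex 1 Grade 2 limit of 3 × ULN, and Grade 1 is empty, so the non-significant branch gives no grade. The significant branch gives at least Grade 1. The order is right.
2. ALT 8 × ULN lies in the range above 5 to 20 × ULN, hence Grade 3. Table 3 Grade 3 needs incapacity or marked limitation, with treatment required. A symptom-free participant does not fit that wording, so the significant branch stops at Grade 1 or 2. The order is reversed by 3 − 1 = 2 grades, or 3 − 2 = 1. AST has the same limits and behaves the same way.
3. Platelets of 20,000/mm³ lie below the 25,000 limit for Grade 4. On a literal reading of Table 3 they are Grade 1 when silent and untreated, a gap of 4 − 1 = 3. The paragraph on serious or life-threatening AEs closes that gap if the clinician so judges.

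The second check compares Annex 1 with its own title. Haemoglobin Grade 3 in Table 6 joins a limit of 8.0 g/dL to an indication for transfusion, although the exclusion criteria treat a level below 8 g/dL as moderate to severe anaemia. Sodium and potassium Grade 3 cells presuppose admission. The hyperglycaemia row is defined wholly by clinical action, including the start of insulin. A value without clinical significance cannot meet such descriptions, so title and content conflict without any hypothetical case.

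**The case against.** Several points on the other side have weight.

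- *The significant branch has safeguards.* Table 3 is to be used primarily, not exclusively. Events judged serious or life-threatening become Grade 4. The medical monitor makes a final eCRF review for participants with an AE. These narrow the problem. They do not remove it: no other scale is named for significant values, and the Grade 4 rule does not reach a silent ALT of 8 × ULN that nobody calls serious.
- *A significant finding leads to medical care* (Screening visit), so Grade 1 is less likely. This stands in part. Minimal intervention could justify Grade 2, which is still below Annex 1's Grade 3.
- *No investigator would call 8 × ULN insignificant.* Perhaps. Then the numeric limits for Grades 3 and 4 go unused where they matter most.

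A reader might also infer more than the protocol supports.

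- *That the safety comparison between arms is lost.* It is not. Secondary endpoint 3 is the occurrence of AEs, the Assessment of safety section speaks of frequency, incidence and nature, and the Statistics section plans descriptive summaries. Laboratory data are recorded in the CRFs, so values can be tabulated or regraded later.
- *That every analyte is affected, always in the wrong direction.* Hyperglycaemia has no numeric limits, LDH has limits only at Grade 2, and mild values can be ordered correctly.
- *That a potassium above 7.0 mmol/L judged not significant must be reported as an SAE.* The SAE note on Grade 4 belongs to Table 3, Annex 1 carries none, and SAEs are defined by outcome. The protocol is simply silent on whether an Annex 1 Grade 4 carries that duty.

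**Conclusion.** The concern holds in a limited form. For analytes with numeric Annex 1 limits, the stated rule can give an identical value a lower grade because it was judged significant. For symptom-free ALT or AST above 5 to 20 × ULN the reversal is one or two grades. For values in a numeric Grade 4 range it can reach three on a literal reading, unless the clinician invokes the serious or life-threatening rule. Separately, Annex 1 contradicts its own title.

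This rests on Table 3 being applied as worded to participants without symptoms. The protocol gives no expected rate of such values at D3 and D7, so the number of events affected among the 44 participants cannot be stated. The harm is to the recorded severity of laboratory AEs. It does not reach AE occurrence, the primary endpoint, the sample size or any planned test. It should be corrected, because it is a rule fixed in the protocol and not a detail left for the analysis plan.

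**What to change.** Reconcile Table 3, the Laboratory safety section and Annex 1 so that one value gets one grade:

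- Apply Annex 1's numeric limits wherever they exist, whatever the clinical significance.
- Record clinical significance as a separate yes/no item.
- Grade any associated clinical event separately by Table 3.
- Keep Table 3 for clinically significant values that Annex 1 gives no number for. These are analytes without a row (GGT, conjugated bilirubin, calcium, magnesium), hyperglycaemia, cells without a number such as haemoglobin Grade 4, and values milder than the lowest Annex 1 limit.
- Remove the restriction to values that are not clinically significant from the annex title. The cells that describe consequences then no longer conflict with it.

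The cost is protocol wording and guidance on the AE form, with no extra tests. Slightly more high-grade laboratory events may be listed.
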